#### **9.3.6. Other Analyses**

A concentration-response analysis will be performed according to International Council for Harmonisation (ICH)-E14 (the clinical evaluation of QT/QTc interval prolongation and proarrhythmic potential for non-antiarrhythmic drugs) guidelines.

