### 5.11.6 Electrocardiogram Data

Descriptive statistics for observed values and changes from baseline in the following ECG variables will be tabulated at each follow-up:

- Heart rate (bpm)
- PR interval (ms)
- QRS complex (ms)
- QT interval (ms)
- QTc interval (ms)
- QTcF interval (ms) [Fridericia's formula]
- QTcB interval (ms) [Bazett's formula]
- RR interval (ms)

QMD Ref: Worldwide-TMP-ST-054-1.0_Effective: 12Aug2022	Governing QMD: Worldwide-SOP-ST-026
Confidentiality Statement This document is the property of Worldwide Clinical Trials Inc. and may not be duplicated, copied, altered or removed from company without prior approval from Worldwide Quality Assurance or in compliance with Worldwide Standard Operating Procedures.	

Worldwide Clinical Trials Controlled Quality Management Document		
 WORLDWIDE CLINICAL TRIALS	Sponsor:	Eli Lilly and Company
	Protocol Number:	J4N-MC-YFAA
STATISTICAL ANALYSIS PLAN		

Number and percentage of subjects that meet each of the following categories will be presented:

- Largest postdose assessment of QTcF > 450
- Largest postdose assessment of QTcF > 480
- Largest postdose assessment of QTcF > 500
- Largest QTcF change from baseline > 30
- Largest QTcF change from baseline >60

Shift tables in relation to the overall interpretation (Normal; Abnormal Not Clinically Significant [NCS], and Abnormal Clinically Significant [CS]) from baseline to each follow-up visit will be presented.

The relationship between plasma PK concentrations of LY3885125 and  $\Delta$ QTcF will be quantified using a linear mixed-effects modelling approach. The model will have  $\Delta$ QTcF as the dependent variable, plasma PK concentrations of LY3885125 as the explanatory variate (0 for placebo), baseline QTcF as an additional covariate, study treatment (active = 1 or placebo = 0) and time (i.e., post-dose time point: categorical) as fixed effects, and random effects on intercept and slope per participant. In all calculations, concentrations in participants who received placebo will be set to zero. LY3885125 plasma PK concentrations below the quantifiable limit at pre-dose will be set to zero and after dosing will be set to 1/2 the lower limit of quantitation in the concentration-QTc analysis.

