An unstructured covariance matrix will be specified for the random effects. If convergence cannot be achieved even after appropriate rescaling of the concentrations, the random effect on the slope and intercept will be dropped, in this order, until convergence is achieved. The degrees of freedom (df) estimates will be determined by the Kenward-Roger method. From the model, the slope (i.e., the regression parameter for the concentration) and the treatment effect-specific intercept (defined as the difference between active and placebo) will be estimated together with the 2-sided 90% CI. The estimates for the time effects will be reported with standard error (SE).

The following SAS codes can be used to conduct the LME model in the example:

```
proc mixed data=PKQTc method=reml;
  class USUBJID AVISTPT;
  model  $\Delta$ QTcF=PRTAN CONC1 AVISTPT CBASE / solution cl noint alpha=0.1
    alphap=0.1 covb ddfm=kr;
  random int CONC1 / type=un subject=USUBJID s;
run;
```

Throughout the LME modelling, for any timepoints where triplicate values are collected for QTcF, then the arithmetic average of the triplicates should be analysed.

QMD Ref: Worldwide-TMP-ST-054-1.0_Effective: 12Aug2022	Governing QMD: Worldwide-SOP-ST-026
Confidentiality Statement	
This document is the property of Worldwide Clinical Trials Inc. and may not be duplicated, copied, altered or removed from company without prior approval from Worldwide Quality Assurance or in compliance with Worldwide Standard Operating Procedures.	

Worldwide Clinical Trials Controlled Quality Management Document		
 WORLDWIDE CLINICAL TRIALS	Sponsor:	Eli Lilly and Company
	Protocol Number:	J4N-MC-YFAA
STATISTICAL ANALYSIS PLAN		

A scatter plot of QTcF data vs LY3885125 plasma PK concentration will also be presented for all timepoints where an ECG and PK sample were drawn within the same 10 minute window, with unique formatting for each treatment group.

All ECG data, including details of any abnormalities, will be listed.

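### SAP 5.11.6: the last convergence fallback in the concentration-QTc model drops the participant random intercept, so if it is ever reached the 90% CIs ignore within-participant correlation (low priority, contingent)

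*SAP*

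**What the plan says.** Protocol 9.3.6 commits to the analysis: "A concentration-response analysis will be performed according to International Council for Harmonisation (ICH)-E14". SAP 5.11.6 specifies it as a linear mixed model for change in QTcF, with treatment, concentration and baseline QTcF as covariates, "time (i.e., post-dose time point: categorical) as fixed effects", and "random effects on intercept and slope per participant". The covariance of the random effects is unstructured.

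The slope and the active-minus-placebo intercept "will be estimated together with the 2-sided 90% CI". On inference the SAP adds: "The degrees of freedom (df) estimates will be determined by the Kenward-Roger method". Where ECGs are taken in triplicate, "then the arithmetic average of the triplicates should be analysed".

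For non-convergence after rescaling the rule is that "the random effect on the slope and intercept will be dropped, in this order, until convergence is achieved". In the sample SAS code the only statement linking records from one participant is "random int CONC1 / type=un subject=USUBJID s". Neither the text nor the code gives a residual covariance structure, a robust variance, or a minimum model below which the rule may not go.

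**The concern.** Each participant is randomised once and contributes change in QTcF at several post-dose times, so the records are clustered. The random effects are the only part of the model that recognises this. Taken to its end, the rule leaves a fixed-effects regression with independent errors. Kenward-Roger then has no covariance structure to adjust for, and the degrees of freedom become the residual ones. Averaging triplicates removes replication within a time point but not correlation across time points.

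Treatment varies only between participants, with about 10 on placebo, so the active-minus-placebo intercept is the estimate most exposed. It and the slope are the only QT results in the SAP that carry confidence intervals. An interval that is too short could make a chance imbalance among the placebo participants look like a drug effect, or bound a QT effect too tightly.

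**Working it through.** **Participants.** Protocol 4.1.1 and 9.5 give 2×(6+2) + 3×(9+2) + (10+9) = 16 + 33 + 19 = 68, which reproduces the stated total of about 68. SAP section 3 says Cohort 6 was not enrolled, so 68 − 19 = 49: active 6+6+9+9+9 = 39, placebo 5×2 = 10. (The 30 shown for Cohorts 1 and 2 in the SAP section 4 table fits neither 6:2 nor 68 and looks like a misread redaction; 8 per cohort is used. Placebo is included, as the model text requires.)

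**Assumptions not in the documents.** Post-dose times T = 8 (6, 10 and 13 also tried); ICC 0 to 0.7; total SD of change in QTcF 8 ms; illustrative concentration profiles; no true drug effect.

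**Approximate formula.** For a between-participant contrast analysed as if records were independent:

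- design effect D = 1 + (T − 1)×ICC
- reported SE / true SE = 1/√D
- actual coverage of a nominal 90% CI = 2Φ(1.645/√D) − 1

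| ICC (T = 8) | D | SE ratio | Coverage by formula | Intercept coverage, simulated | Slope coverage, simulated |
|---|---|---|---|---|---|
| 0.05 | 1.35 | 0.86 | 84% | 84-86% | 87-89% |
| 0.2 | 2.40 | 0.65 | 71% | 71-73% | 79-80% |
| 0.5 | 4.50 | 0.47 | 56% | 56-57% | 67-71% |

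The simulations fit the SAP's fixed effects (treatment, concentration, categorical time, baseline) with no random effects.

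**Other numbers of time points.** Simulated intercept coverage was 76% at T = 6, ICC 0.2; 60% at T = 10, ICC 0.4; and 45% at T = 13, ICC 0.6. The SE ratios were 0.71, 0.49 and 0.35, against 0.71, 0.47 and 0.35 from the formula. At ICC 0 both intervals covered 89-93%.

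**Why the slope differs.** Its interval without random effects is about as wide as with a random intercept (SE ratio 0.86 to 1.22 for ICC 0.2 to 0.6). It under-covers because the estimate itself is less precise. At T = 10, ICC 0.4, the reported SE is 2.57 and the true one 4.49; with the random intercept kept they are 2.82 and 2.84 (arbitrary concentration units).

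**Random intercept kept, slope dropped.** For ICC 0.2 to 0.6 and T = 6 to 13, coverage was 88-92% for the intercept and 87-90% for the slope. With true slope variation that the model ignored (ICC 0.4, T = 6 and 10), it was 90-91% and 87-88%.

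**How often the last step might be reached.** With T = 8 and 2,000 runs per ICC, the random-intercept fit had no optimiser failures in 14,000 fits (ICC 0 to 0.5). This used a one-dimensional optimiser, not PROC MIXED. As the nearest proxy for trouble, the intercept variance was estimated as zero in 52% of runs at ICC 0, 27% at 0.02, 7% at 0.05, 0.4% at 0.1, and none from 0.2 to 0.5.

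**The case against.** The strongest reply is that the rule stops at the first model that converges. Harm requires the random-intercept model, with its single variance component, to fail too, and the settings with 56-73% coverage are those where no sign of failure appeared. Where the intercept variance was estimated as zero, coverage without random effects was still 87-89%, and a fit with zero variance is the same as ordinary regression anyway. This stands, and it is why the priority is low. It does not make the last step valid: a prespecified rule should not end in a model that is wrong whenever clustering is present.

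Three stronger readings are tempting and not supported.

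- *The analyst may choose to drop the intercept.* The SAP fixes the order and the stopping condition; it gives no discretion.
- *The planned QT intervals are far too narrow.* Only the last step is affected, the size depends on an unknown ICC, and the slope suffers less than the intercept. The larger residual degrees of freedom hardly matter: with 49×8 = 392 records and 11 parameters the 90% critical value is 1.65 on 381 df, against 1.68 on 46.
- *The QT false-positive rate is inflated.* SAP 5.11.6 specifies estimates with CIs, not a QT test or a decision threshold, and Protocol 9.3.5 rules out statistical comparisons for safety endpoints. QTcF threshold counts, shift tables, the scatter plot and listings do not depend on this model.

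The SAS code is offered as an example, so the missing REPEATED statement alone would be weak evidence. The accompanying text, however, describes no other within-participant covariance either.

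**Conclusion.** Wrong as written, with low priority and contingent effect. The prescribed final fallback treats correlated QTcF changes as independent. If it were reached with real within-participant correlation, the intercept CI would fall short of its nominal 90% by about 4-6 percentage points at ICC 0.05, 17-19 at 0.2 and 33-34 at 0.5; for the slope CI the shortfall would be about 1-3, 10-11 and 19-23 points. These figures rest on the assumed 8 time points and ICC values, 49 participants split 39 to 10, and illustrative concentrations. They describe coverage given that the step is used. They are not a forecast for the reported analysis, and no probability of PROC MIXED reaching the step can be derived from the documents.

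**What to change.** Replace the fallback rule in SAP 5.11.6 with:

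> If convergence is not achieved after rescaling, the random slope will be dropped; the participant random intercept will be retained. If the random-intercept model does not converge, a marginal model with compound-symmetry within-participant covariance (`REPEATED / subject=USUBJID type=cs`) will be fitted. The step used will be reported.

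Keep Kenward-Roger degrees of freedom throughout. Compound symmetry implies the same covariance as a random intercept when the correlation is positive; its added value is that it also allows zero or negative correlation, the boundary case in which a random intercept is most likely to give trouble. Trying `type=vc`, which keeps both random effects but drops their covariance, before removing the slope is optional.

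The cost is a short wording change and one alternative PROC MIXED statement, with no new data. Results are unchanged if the planned model converges. Under SAP section 5 the change can be made before Part A database lock, or documented in the post-lock addendum.

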	14.3.4.6.3	Safety ECG Data, Overall Interpretation Shift from Baseline to Worst Post Baseline, Part A – Safety Analysis Set	IP	-
	14.3.4.7.1	Prior Medications by ATC Level 3 and Preferred Name, Part A – Full Analysis Set	IP	-
	14.3.4.7.2	Concomitant Medications by ATC Level 3 and Preferred Name, Part A – Full Analysis Set	IP	14.3.4.7.1
	14.3.4.8.1	PCSK9 Data, Descriptive Statistics for Observed Values and Change from Baseline, Part A – PD Analysis Set	IP	-
	14.3.4.8.2	Apo Panel Data, Descriptive Statistics for Observed Values and Change from Baseline, Part A – PD Analysis Set	IP	14.3.4.8.1
	14.3.4.8.3	CCI [REDACTED] [REDACTED] [REDACTED] – [REDACTED]	IP	14.3.4.8.1
	14.3.4.9	Linear Mixed-Effects Model for Plasma PK Concentrations of LY3885125 and ΔQTcF, Part A – PK Analysis Set	Stat IP	-
	14.3.4.10	Summary of Immunogenicity Parameters by Treatment Group – Immunogenicity Analysis Set	IP	-
14.4.1	PK Analysis			
	14.4.1	Descriptive Statistics for Concentration-Time Data of LY3885125 in Plasma after Single Ascending Subcutaneous Doses of LY3885125 – PK Analysis Set	IP	-

QMD Ref: Worldwide-TMP-ST-054-1.0_Effective: 12Aug2022	Governing QMD: Worldwide-SOP-ST-026
Confidentiality Statement This document is the property of Worldwide Clinical Trials Inc. and may not be duplicated, copied, altered or removed from company without prior approval from Worldwide Quality Assurance or in compliance with Worldwide Standard Operating Procedures.	

Worldwide Clinical Trials Controlled Quality Management Document		
 WORLDWIDE CLINICAL TRIALS	Sponsor:	Eli Lilly and Company
	Protocol Number:	J4N-MC-YFAA
STATISTICAL ANALYSIS PLAN		

Section Number	Table Number	Table Title	Validation Method	Shell Number (if repeat)
	14.4.2	LY3885125 Plasma Pharmacokinetic Parameters after Single Ascending Subcutaneous Doses of LY3885125 – PK Analysis Set	IP	-
	14.4.3	Amount of LY3885125 Excreted in Urine per Collection Interval – PK Analysis Set	IP	-
	14.4.4	Percentage of LY3885125 Dose Excreted in Urine per Collection Interval – PK Analysis Set	IP	-
	14.4.5	LY3885125 Urine Pharmacokinetic Parameters after Single Ascending Subcutaneous Doses of LY3885125 – PK Analysis Set	IP	-
	14.4.6	Dose-Proportionality Assessment of LY3885125 in Plasma after Single Ascending Subcutaneous Doses of LY3885125 – PK Analysis Set	MR	-

QMD Ref: Worldwide-TMP-ST-054-1.0_Effective: 12Aug2022	Governing QMD: Worldwide-SOP-ST-026

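### The concentration-QTc model reports a slope and an intercept, but no predicted placebo-corrected QTcF effect at the concentrations reached

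*SAP*

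**What the plan says.** Protocol 9.3.6 says: "A concentration-response analysis will be performed according to International Council for Harmonisation (ICH)-E14". It names no effect measure, concentration or threshold.

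SAP 5.11.6 gives the model. The relationship between concentration and ΔQTcF "will be quantified using a linear mixed-effects modelling approach". The fixed terms are treatment (1 active, 0 placebo), concentration (0 for placebo), categorical post-dose time and baseline QTcF. Intercept and slope are random by participant. The section then lists what is taken from the fit: the concentration slope and, in the SAP's words, "the treatment effect-specific intercept (defined as the difference between active and placebo) will be estimated together with the 2-sided 90% CI". Time effects are reported with a standard error.

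The example code asks for coefficients with 90% limits ("solution cl noint alpha=0.1") and for the covariance matrix of the fixed effects ("alphap=0.1 covb ddfm=kr"). It contains no ESTIMATE statement.

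The output list in SAP section 10 has one table for this model, 14.3.4.9, titled "Linear Mixed-Effects Model for Plasma PK Concentrations of LY3885125 and ΔQTcF, Part A" and assigned to the PK Analysis Set. Figure 14.3.7.1 is a scatter plot of QTcF data against concentration, not a model prediction.

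**The concern.** The size of a QT effect is read from the placebo-corrected ΔQTcF at the exposures the doses produce. The fitted model contains that quantity, but the plan stops at its two components. The intercept is the active-minus-placebo difference extrapolated to zero concentration. The slope is a change per unit of concentration. Neither is the effect at Cmax of any dose.

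A reader with only the two published intervals can add the point estimates, but cannot form a correct interval for the sum. If an effect is shared between the two terms, each can look unremarkable while their sum does not. If the effect measure and the concentrations are not fixed in advance, both would be chosen after the data are seen.

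**Working it through.** **Plan's own figures.** The documents give no precision, power or threshold for the QTc model, so there is no QTc figure to reproduce. The only relevant count is the approximate Part A total of 68 (Protocol 9.5). Reading the allocation ratios as head counts gives 2×(6+2) + 3×(9+2) + (10+9) = 68, which agrees. SAP section 3 says Cohort 6 was not enrolled. That leaves 2×8 + 3×11 = 49: 2×6 + 3×9 = 39 active and 5×2 = 10 placebo.

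**Effect and its standard error.** With b_T the treatment intercept and b_C the slope:

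- D(C) = b_T + b_C × C
- SE[D(C)]² = Var(b_T) + C² Var(b_C) + 2C Cov(b_T, b_C)

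The last term cannot be recovered from the two separate intervals.

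**Assumptions (redacted or not given in the documents).** I assumed seven post-dose times and three relative dose patterns (1-3-10-20-40, 1-2-4-6-8 and 1-4-16-32-64). The random-intercept, random-slope (at top-dose Cmax) and residual SDs were 4/0/5, 5/3/6 or 7/4/8 ms. Limits are normal 90% limits (1.645); Kenward-Roger limits would be somewhat wider.

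Generalised least squares for the SAP's fixed and random effects gives, for the first dose pattern:

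| SDs (ms) | SE b_T | SE b_C × Cmax | Corr. | SE D(Cmax) | 90% half-width |
|---|---|---|---|---|---|
| 4/0/5 | 1.62 | 1.61 | −0.21 | 2.03 | 3.34 |
| 5/3/6 | 2.01 | 2.31 | −0.23 | 2.69 | 4.43 |
| 7/4/8 | 2.80 | 3.11 | −0.21 | 3.72 | 6.12 |

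Middle row: 2.01² + 2.31² − 2×0.23×2.01×2.31 = 4.04 + 5.34 − 2.14 = 7.24, and √7.24 = 2.69. Leaving out the covariance gives √9.38 = 3.06, which is 14% too large. Over all nine combinations the half-width is about 3.2 to 6.3 ms, and leaving out the covariance overstates the SE by about 12 to 21%.

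**Illustration: true effect 10 ms at top Cmax, 5 ms from each term.**

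- Slope interval covers zero. Middle row: 5/2.31 = 2.16; 2.16 − 1.645 = 0.52; 1 − Φ(0.52) = 30%. The first row gives 7% and the third 51%.
- Predicted-effect interval excludes zero. Middle row: 10/2.69 = 3.72; 3.72 − 1.645 = 2.07; Φ(2.07) = 98%. The first row gives 99.95% and the third 85%.

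Over the nine combinations the extremes are 6% and 52% for the slope, and 84% and just above 99.9% for the predicted effect. Because the inputs are assumed, I quote these as roughly 6 to 50% and roughly 85 to 99.9%.

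**Can the planned table support the contrast?** SAP 5.1.5 limits the PK Analysis Set to participants dosed with LY3885125. On that set the treatment column is 1 in every row, and so are the summed time indicators. The design has 10 columns (treatment, concentration, seven times, baseline) and rank 9. With placebo participants included, the rank is 10. On the PK Analysis Set, neither b_T as defined nor D(C) can be estimated.

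**The case against.** The case against has real weight. Protocol 9.1 plans no inferential analyses and defines no hypotheses, and Protocol 9.3.5 rules out statistical comparisons of treatment groups for safety endpoints. The model's stated aim is to quantify a relationship, and the slope does that. Other QT outputs are planned: QTcF values and changes from baseline, counts above 450, 480 and 500, changes above 30 and 60, and shift tables, with dose groups shown beside pooled placebo. The covariance is already printed and geometric mean Cmax is already planned, so the effect can be derived later. The table shells and the cited modelling paper cannot be seen here. The trial stopped after Cohort 5, so no later dosing decision within it depends on this model.

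All of that stands, and it limits the point to reporting. It does not close the gap. SAP 5.11.6 says what is taken from the model, and the predicted effect is not on that list. A descriptive analysis should still state the quantity of interest.

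A reader might infer more than the documents support:

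- That the two 90% intervals act as two tests with an inflated false-signal rate, about 1 − 0.9² = 19%. No rule says that an interval excluding zero is a signal.
- That slope and intercept conflict, or that the plan leaves QT unaddressed. The coefficients measure different things, and the descriptive outputs exist.
- That placebo data are meant to be left out of the model. The text of 5.11.6 sets placebo concentrations to zero, so it intends to use them. The analysis set named for the table contradicts that text.

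**Conclusion.** The point holds as a reporting gap. The plan fits a model that contains the placebo-corrected QTcF effect at the concentrations reached, but reports only its components and makes no use of the covariance needed for its interval. That the effect is intercept + slope × C, and that its interval needs the covariance, follows from the SAP's model without outside assumptions. So does the finding that the PK Analysis Set cannot support the contrast.

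The percentages illustrate how far the slope interval and the predicted-effect interval can differ. They depend on the assumed SDs, sampling times and dose spacing, and on an equal split of the effect. They are not error rates of any planned decision. I rate this a worthwhile, inexpensive improvement to a descriptive safety analysis.

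**What to change.** Before Part A database lock, amend SAP 5.11.6 as follows. If lock has passed, use the post-lock addendum that SAP section 5 provides for.

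1. Name as the main reported effect measure the model-predicted active-minus-placebo ΔQTcF at the geometric mean Cmax of each dose level. Make the highest dose the main row and give a 2-sided 90% CI.
2. Add one labelled statement per dose to the code, for example `estimate 'label' PRTAN 1 CONC1 <gmCmax> / cl alpha=0.1;`. If concentrations are rescaled for convergence, as the SAP allows, put Cmax on the same scale.
3. Add these rows to Table 14.3.4.9 and present slope and intercept as supporting model parameters.
4. Assign that table to an analysis set that includes placebo participants, with concentration set to 0 as 5.11.6 already states. Without this, neither the planned intercept nor the new rows can be estimated.

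No new data or procedures are needed. The cost is SAP wording, a changed analysis-set label, five statements for the five doses and a few more table rows.

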### 5.11.7 Physical Examination

Physical examination data will maintained at the SDTM level, but will not be presented in any tables or listings. Details of any consequential findings will be visible in medical history or AE outputs.

